6. RESEARCH PLAN AND METHODS

6.1 Research design

This is a two-arm pilot RCT with embedded feasibility study that will be undertaken as a phased programme of work comprising of intervention testing and feasibility work (Phase 1) and a pilot trial with a process evaluation (Phase 2). In line with MRC guidance on the development and evaluation of complex interventions [6] we have included a preliminary phase, which focuses on intervention refinement and feasibility and a qualitative process evaluation of the pilot RCT in order to ensure that both the intervention and trial procedures are optimised and can be incorporated into routine clinical practice, thus increasing the likelihood that a full-scale trial will generate the desired outcomes [7]. The study will be conducted according to recommendations for good practice in pilot studies [48].

6.2 Sampling

6.2.1 Cancer patient study participants

Adults who have been, i) diagnosed with primary colorectal cancer, and ii) are in the recovery period following surgery and may or may not be receiving adjuvant chemotherapy.

6.2.2 Exclusion criteria

Adults who i) have advanced disease, or ii) fail clinical/risk assessment for rehabilitation and therefore deemed by clinicians as unsafe to participate in exercise classes, (e.g. according to recent guidance patients with severe anaemia should delay exercise and patients with compromised immune function should avoid public gyms and exercise classes [49]), or iii) have a severe cognitive impairment and therefore unable to give informed consent to participate in the study, or iv) are unable to communicate in English (N.B. if this study shows that the intervention and trial procedures are acceptable and feasible then translation service costs will be requested in a future large scale trial).

6.2.3 Sample size

As this is a pilot RCT with embedded feasibility study, a formal power calculation is not appropriate; the study is not powered to detect a clinically meaningful difference in the primary outcome between the rehabilitation and usual care groups. Rather the aim is to provide robust estimates of the likely rates of recruitment and retention, and to yield estimates of the variability of the primary and secondary outcomes to inform power calculations for a future large-scale trial. We will therefore use the pilot trial (Phase 2 of the proposed study) in order to provide a quantitative estimate of the intervention impact (relative to control) in order to inform the sample size estimation for a definitive trial. While we recognise that the number of patients to be included in a pilot study will depend on the parameters to be estimated, a general rule of thumb is to take a minimum of 30 patients to estimate a parameter [37], which we believe is achievable

in this study. For the pilot RCT (Phase 2), we believe that over 6 months across the 3 sites we will be able to approach 250 patients. From their responses we will be able to determine whether it is possible to recruit patients and also estimate eligibility, consent, participation and retention rates and speed of recruitment for a future large scale trial. We have conservatively estimated that we will recruit approximately 66 patients. Cancer clinicians estimate that approximately one third will be ineligible (e.g. have advanced disease) and based on recruitment to a RCT about physical activity with cancer patients in Scotland (27% recruitment rate) [50] and a trial involving colorectal cancer patients within 3 months of completing surgery conducted in Canada (35% recruitment rate) [51] we estimate that about a third of eligible patients will consent. Thus, we estimate that in Cardiff and Stirling 26 patients in each site will be recruited (13 intervention group and 13 control group). In Inverness, we estimate that 14 patients will be recruited (7 intervention group and 7 control group). However, a recruitment rate of 71 per cent, which was achieved in a study of a personalised lifestyle programme for colorectal cancer survivors in Scotland [34], would provide a total of 118 patients.

For the feasibility study (Phase 1) we will recruit 12 colorectal cancer patients from one site to assess the feasibility and acceptability of the intervention, recruitment processes for the trial and study instruments. Six cardiac patients and 6 clinicians will also be recruited to assess the feasibility and acceptability of the intervention and recruitment processes.

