This is a two-arm pilot RCT with embedded feasibility study that will be undertaken as a phased programme of work comprising of intervention testing and feasibility work (Phase 1) and a pilot trial with a process evaluation (Phase 2). This design is in line with MRC guidance on the development and evaluation of complex interventions [6] to ensure that both the intervention and trial procedures are optimised and can be incorporated into routine clinical practice [7]. Sample

The sample size in Phase 1 is 12 cancer patients and their nominated family member, 6 cardiac patients and 12 clinicians. In Phase 2 the estimated sample size is 66 colorectal cancer patients.

Research sites

The study will be conducted in three cardiac rehabilitation facilities in NHS Highland, NHS Wales and Forth Valley: i) Highland Heartbeat Centre, Raigmore Hospital, ii) University Hospital of Wales and Maindy Sports Centre, Cardiff, and iii) NHS Hub at the Peak sports and leisure complex, Stirling.

Cancer Patient Eligibility

Adults who have been i) diagnosed with primary colorectal cancer, and ii) are in the recovery period following surgery; and may or may not be receiving adjuvant chemotherapy.

Exclusion criteria

Adults who: i) have advanced disease; or ii) fail clinical/risk assessment for rehabilitation and therefore deemed by clinicians as unsafe to participate in exercise classes; or iii) have a severe cognitive impairment and are therefore unable to give informed consent to participate in the study; or iv) are unable to communicate in English.

Intervention

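### The Phase 2 recruitment estimate of 66 does not follow from its own inputs, which give about 56 (45 to 58 on the two cited base-case rates)

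*Protocol*

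**What the plan says.** Protocol section 6.2.3 builds the Phase 2 estimate as a recruitment funnel. The study team expects that "over 6 months across the 3 sites we will be able to approach 250 patients". On eligibility, "Cancer clinicians estimate that approximately one third will be ineligible (e.g. have advanced disease"). On consent, "we estimate that about a third of eligible patients will consent", a figure based on two earlier trials with recruitment rates of 27% and 35%. The result is given as "We have conservatively estimated that we will recruit approximately 66 patients", divided into 26 at Cardiff, 26 at Stirling and 14 at Inverness, with equal numbers per arm at each site. The paragraph closes with an optimistic scenario: a 71% rate, seen in a Scottish lifestyle study, would give 118.

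The SAP's Sample Size section repeats all of this, with numbered sites in place of names. The protocol summary (section 2) states "In Phase 2 the estimated sample size is 66 colorectal cancer patients", and section 12.2.3 (Intervention costs) refers to 66 as the target. Section 6.2.3 of the protocol also says that "a general rule of thumb is to take a minimum of 30 patients to estimate a parameter"; the SAP does not repeat that rule.

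**The concern.** The output and all the inputs stand in one paragraph, and they do not agree. The number is also described as conservative, so a reader would expect it to lie at or below what the cited rates imply. It lies above both.

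Recruitment is something this pilot sets out to measure. Objective 5 covers eligibility, consent, recruitment and retention rates and speed of recruitment, and section 5 asks whether centres could recruit enough patients for a large trial. If observed recruitment is set beside 66, a study in which every assumption proved right would appear about 10 patients short, and the reader would not know that the gap came from the forecast.

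**Working it through.** **Inputs (Protocol 6.2.3; same in the SAP, Sample Size)**

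- Approached: 250
- Ineligible: about 1/3
- Consent among eligible patients: about 1/3, from cited rates of 27% and 35%
- Optimistic rate: 71%, stated to give 118
- Stated estimate: 66, as 26 + 26 + 14 by site and 13 + 13 + 7 = 33 per arm

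**Formula:** recruited = approached x (1 - proportion ineligible) x consent rate.

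**Step 1. Find the denominator from the plan's other figure.** Eligible = 250 x 2/3 = 166.7. At 71%: 166.7 x 0.71 = 118.3, which reproduces the stated 118. The plan therefore applies its rates to about 167 eligible patients.

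**Step 2. Apply the base-case rates to the same denominator.**

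| Consent among eligible | Total | Per arm |
|---|---|---|
| 27% (lower cited rate) | 45.0 | 22.5 |
| 31% (mean of the two) | 51.7 | 25.8 |
| 1/3 (planning value) | 55.6 | 27.8 |
| 35% (higher cited rate) | 58.3 | 29.2 |
| Stated | 66 | 33 |

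The stated figure is 66 / 55.6 = 1.19 times the derived one, about 19% or 10 patients higher.

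**Step 3. Ask what would give 66**, changing one input at a time:

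- Consent: 66 / 166.7 = 39.6%
- Approached: 66 / (2/3 x 1/3) = 297
- Ineligible: 1 - 66 / (250 x 1/3) = 20.8%

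The site split has the same problem. At 2/9 recruited per patient approached, 26, 26 and 14 need 117 + 117 + 63 = 297 approached, not 250.

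**Step 4. Test looser readings.** Rounding generously, with 30% ineligible and 35% consenting, gives 250 x 0.70 x 0.35 = 61.2, still short. The one near match is 250 x 0.27 = 67.5. It omits the ineligibility step that the text states, and on that base 71% would give 177.5, not 118.

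**The case against.** The strongest reply is that this is a hedged forecast in a feasibility study. The inputs are worded as approximations, the documents disclaim a formal power calculation, and rates will be estimated from observed counts whatever number was forecast. Most of that stands, and it limits the severity. It does not remove the inconsistency, because generous rounding reaches only about 61.

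A second reply is that 66 is low beside the 71% scenario, so the word *conservatively* is merely loose. That is true of the comparison with 118. But the text ties 66 to the 27% and 35% trials, and it exceeds what either supports.

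Third, the documents show that output and inputs disagree, not which is wrong. This stands. The sponsor may have had reason to expect about 40% consent or more patients approached, so the fix must leave that route open.

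Several stronger readings are tempting, and the documents do not support them:

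- *That recruiting 56 would count as failure.* No progression criterion or success threshold is tied to 66. The costing section calls it a target, but only for budgeting.
- *That the precision of the pilot's estimates is overstated.* Neither document states a precision for any estimate.
- *That the 30-patient rule is missed.* The rule is not stated per arm. In total, 56 meets it, and so does 45; only a per-arm reading puts 28 below it.
- *That the intervention is under-costed.* Section 12.2.3 budgets for 100 referrals, well above either figure.
- *That numbers after drop-out are inadequate.* The plan gives no attrition rate, and retention is one of the things the pilot is meant to estimate.

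**Conclusion.** The point holds as an arithmetic inconsistency. On the plan's stated inputs, expected Phase 2 recruitment is about 56 (28 per arm), with 45 to 58 on the two cited base-case rates, against a stated 66 (33 per arm). The 26 + 26 + 14 split adds up to 66 correctly but rests on the same unsupported total. Describing 66 as conservative is not justified by the rates it is said to rest on.

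This conclusion assumes only that the rates apply to eligible patients. The wording on consent says so, and the 118 figure confirms it.

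Severity is modest. The error affects no analysis model, analysis population or decision rule. Its practical effect is on how the recruitment result is read when the case for a definitive trial is considered.

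**What to change.** Either of two corrections would resolve it:

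1. Restate expected recruitment as about 56 (45 to 58 on the cited base-case rates; about 28 per arm), and re-derive the site split from the number expected to be approached at each site. The documents do not give those site numbers, so scaling 26 + 26 + 14 down in proportion would be a guess.
2. Keep 66, and state and justify the inputs that give it: about 40% consent among eligible patients, or about 297 approached.

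If the first route is taken, delete *conservatively*. Under the second, the word should also go unless the new inputs support it. Make the same change in the protocol summary (section 2), section 6.2.3, the reference to the target in section 12.2.3, and the SAP's Sample Size section.

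The SAP describes trial conduct largely in the past tense, so the change there should be recorded as a correction to the derivation and not as a lowered benchmark. In the report, set the observed eligibility and consent proportions beside the stated assumptions (one third ineligible, one third of the eligible consenting), instead of comparing the total with 66.

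The cost is wording only. The design, the analysis and the 100 referrals costed are unchanged, and nothing here calls for a larger trial.

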6.3 Setting

The study will be conducted in three cardiac rehabilitation facilities in NHS Highland, NHS Wales and Forth Valley: i) Highland Heartbeat Centre, Raigmore Hospital, ii) University Hospital of Wales and Maindy Sports Centre, Cardiff, iii) NHS Hub at the Peak sports and leisure complex, Stirling.

6.4 Intervention and control (usual care)

The intervention is rehabilitation for colorectal cancer patients in a cardiac rehabilitation setting. An 8/12-week (number of weeks depending on research site) post-hospital rehabilitation programme will be delivered by a member of the cardiac multi-disciplinary team (e.g. cardiac physiotherapist, cardiac nurse or dietician) to a mixed class of cancer/cardiac patients in a cardiac rehabilitation setting with some components specifically tailored for cancer patients and delivered by a cancer nurse. Rehabilitation classes will be delivered twice weekly or once a week depending on research site. The rehabilitation programme comprises 60/90 minutes (depending on research site) of exercise training (aerobic and muscle strengthening) delivered to a mixed class of cancer/cardiac patients by a cardiac physiotherapist who will receive additional training and on-going support by a cancer-exercise specialist.

Participants will set individual physical activity goals with advice and support from the physiotherapist. Cardiac physiotherapists will be pragmatically applying underpinning health behaviour theories by for instance, discussing barriers to engaging in physical activity with patients and goal setting, which is in line with current behaviour change theory [68-71] and cardiac rehabilitation guidance [72]. It is now well recognised that advice, education or information does not lead to lasting change in repetitive health behaviours. It is also universally accepted that increasing physical activity leads to a host of major health benefits, but while many individuals have the best of *intentions* to take more exercise, this does not translate into lasting change in *behaviour*. This is well-recognised as the intention-behaviour gap [73] and why action and coping planning is recommended and will be adopted [74].

The exercise class will be followed by 30/60 minutes (depending on research site) of education (e.g. stress management, diet, drug therapy, smoking cessation, benefits of exercise and relaxation). A member of the cardiac multi-disciplinary team will deliver some educational sessions to a mixed class of cancer/cardiac patients because they are relevant to both cancer and cardiac patients (e.g. smoking cessation, relaxation). A colorectal cancer nurse will deliver some educational sessions (e.g. cancer therapies) to cancer patients. These educational sessions will either be delivered to a group of cancer patients (e.g. when cardiac patients receive a session about drug therapy from a member of the cardiac multi-disciplinary team, cancer patients will receive an equivalent session about drug therapy from a cancer nurse) or one-to-one by telephone (depending on research site). To optimise intervention fidelity, interventionists will be expected to follow the cancer patient rehabilitation pathway (Appendix 1) for this study, and also their site-specific rehabilitation programme. Patients randomised to the control arm of the pilot RCT (Phase 2 of the study) will receive 'Staying healthy after bowel cancer' booklet by Bowel Cancer UK, which includes a section on 'staying fit'.

6.5 Proposed measures

A key purpose of the feasibility study (Phase 1) is to assess the acceptability of the proposed outcome measures for a large scale trial. Primary and secondary outcomes will be measured in Phase 1 before participants attend rehabilitation classes. A key purpose of the pilot study (Phase 2) is to determine completion rates of these proposed outcomes measurement tools which will be measured before participants attend rehabilitation classes (baseline) and follow up (immediately at the end of the rehabilitation programme and 3 months later).

6.5.1 Primary outcome: physical activity

The proposed primary outcome in a future large scale trial will be the difference in an objective measure of physical activity levels between the intervention and usual care (control) group. This will be the primary outcome for which data will be collected in the proposed rehearsal pilot trial to inform sample size calculations for a definitive large scale RCT.

The results of the study will allow us to make an informed judgement as to which measures we would use in a full-scale trial and which one should be the primary outcome.

Physical activity will be assessed using the Actigraph GT1M accelerometer (Actigraph LLC, Pensacola, Florida) [8-10]. Participants will be asked to wear an accelerometer for 7 days on 3 occasions (T0 - before patients are randomised to the intervention or control group; T1 - at the end of the intervention (data will be collected 12 weeks after baseline for patients in the control arm); and T2 - 3 months later). Physical activity will also be assessed subjectively using the long (self-report) version of the International Physical Activity Questionnaire (IPAQ) to ascertain the types of activities participants engaged in as this information is not provided by the accelerometers[6; 12].

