6.6 Data collection for Feasibility study (Phase 1)

The purpose of the feasibility study is to evaluate and refine the intervention and main components of the trial. To meet Phase 1 study objectives we will carry out the following: cardiac rehabilitation physiotherapists will firstly attend a one-day training course delivered by a cancer-exercise specialist and complete an evaluation form about the

training. Then in one research site (Stirling), 12 cancer patients will be screened, recruited and referred for rehabilitation. The proposed outcomes and processes will be measured using the instruments we aim to use in a larger scale trial. Patients will be allocated to the next available rehabilitation class, which means that all 12 cancer patients are unlikely to attend the same classes. Patients will then attend a 10 week rehabilitation programme in a cardiac rehabilitation setting. A screening and recruitment log will be completed by a researcher to document all patients considered for the study and subsequently included or excluded at each stage of the recruitment process and reasons given. This will include information such as; when the patient was given information about the study, referred to cardiac rehabilitation, attended for clinical/risk assessment, and received an offer to attend rehabilitation classes. A researcher will also complete an intervention record log to document the number of classes attended by participants, type and duration of exercises, and which education classes the patient attended. On completion of rehabilitation, semi-structured face-to-face interviews will be conducted with, i) 12 cancer patients and a nominated family member, ii) 6 cancer and 6 cardiac clinicians who were involved in screening, recruitment, referral and/or delivering the intervention, and iii) 6 cardiac patients involved in the mixed cancer/cardiac patient rehabilitation classes, in order to gather responses about the acceptability of the intervention and trial procedures. Further description about data collection for Phase 1 is provided below.

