6.9.2 Further impacts on health care use

At each assessment with patients in both rehabilitation and usual care groups, we will ask them to report on: general practitioner visits; hospital emergency department visits and hospital admissions; visits to allied health departments such as physiotherapy and occupational therapy, nutrition, social work and vocational rehabilitation. Patients will also be asked to report on any medications used. A schedule of relevant items will be constructed about which we will ask questions on frequency of use in the previous three months (to match times of regular follow-up proposed in the main trial. Data on hospital visits and drug use will also be available through NHS records. The above items will be costed at NHS pay and prices or, where appropriate, using other (e.g. market-based) sources. Data on rehabilitation programme costs and those on further impacts will be aggregated and the statistical significance of differences in cost per patient between intervention and control group assessed by appropriate methods depending on the distributional characteristics of the data.

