## **Study Methods**

## **General Study Design and Plan**

The intervention was rehabilitation for colorectal cancer patients in a cardiac rehabilitation setting. An 8/12-week (number of weeks depending on research site) post-hospital rehabilitation programme was delivered by a member of the cardiac multi-disciplinary team (e.g. cardiac physiotherapist, cardiac nurse or dietician) to a mixed class of cancer/cardiac patients in a cardiac rehabilitation setting with some components specifically tailored for cancer patients and delivered by a cancer nurse. Rehabilitation classes were delivered twice weekly or once a week depending on research site. The rehabilitation programme comprised of 60/90 minutes (depending on research site) of exercise training (aerobic and muscle strengthening) delivered to a mixed class of cancer/cardiac patients by a cardiac physiotherapist.

Participants set individual physical activity goals with advice and support from the physiotherapist.

The exercise class was followed by 30/60 minutes (depending on research site) of education (e.g. stress management, diet, drug therapy, smoking cessation, benefits of exercise and relaxation). A colorectal cancer nurse delivered some educational sessions (e.g. cancer therapies) to cancer patients. These educational sessions were either be delivered to a group of cancer patients or one-to-one by telephone

Patients randomised to the control arm of the pilot received 'Staying healthy after bowel cancer' booklet by Bowel Cancer UK, which includes a section on 'staying fit'.

Outcome and process measures were administered on three occasions: i) T0 - before patients were randomised to the intervention or control group, ii) T1 - at the end of the intervention (data was collected 12 weeks after baseline for patients in the control arm) and iii) T2 - 3 months later. Participants were asked to wear an accelerometer for 7 days on 3 occasions (T0 - before patients were randomised to the intervention or control group; T1 - at the end of the intervention (data was collected 12 weeks after baseline for patients in the control arm); and T2 – 3 months later.

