## **Efficacy Analyses**

Scoring for outcomes follows the scoring instructions given for each questionnaire. Where no such instruction is present, the following approach will be taken:

If no more than 20% of questionnaire items are missing, the missing items will be replaced by the mean of the remaining items to build a sum score. Where more than 20% of the items are missing, the sum score will be set to missing.

Data for continuous outcome measures will be assessed for normality prior to analysis. Transformations of the outcome variables will be used where necessary if these are not normally distributed.

Outcomes will be analysed as baseline versus end of intervention (EoI) and baseline versus 3 months after intervention.

Continuous outcome will be using multiple linear regression (i.e. analysis of covariance, ANCOVA). Intervention effect differences will be reported with 95% confidence intervals (CIs) and p-values. The baseline characteristics will be explored for meaningful differences between trial arms. Where these are considered meaningful and important these variables will be entered into a stepwise selection procedure and the primary analysis will be adjusted for these variables if they are statistically selected (usual criteria  $p < 0.05$ ).

Outcome measurements across multiple study visits (baseline, EoI, 3 months) will also be analysed using mixed effects (repeated measures) regression models. Models will include fixed effects for intervention group, time point, and their interaction, plus random effects for each subject to account for repeated measures, and will assume a general covariance structure. Each model will also include fixed effects for baseline values of the outcome, other covariates, in the same way as described above for ANCOVA models.

Ordinal and binary outcomes will be analysed as described above using logistic regression.

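### Wherever programme length plus wait is not 12 weeks, T1 and T2 fall at different times since baseline in the two arms, and the SAP does not correct for this

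*Protocol*

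**What the plan says.** Protocol sections 6.5.1 and 6.7.5 give the same rule: "T1 - at the end of the intervention (data will be collected 12 weeks after baseline for patients in the control arm"), with T2 three months after that. The SAP repeats it in the past tense under General Study Design and Plan: "T1 - at the end of the intervention (data was collected 12 weeks after baseline for patients in the control arm"). The SAP's Efficacy Analyses section then compares "baseline versus end of intervention (EoI) and baseline versus 3 months after intervention".

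Programme length varies. Protocol section 6.4 describes "An 8/12-week (number of weeks depending on research site) post-hospital rehabilitation programme", and the SAP gives the same two lengths for Phase 2. Neither document says which site runs which. Section 6.6 gives a different figure for Phase 1 at Stirling: "Patients will then attend a 10 week rehabilitation programme in a cardiac rehabilitation setting".

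Baseline measures precede randomisation (section 6.7.3), and referral to classes follows it (section 6.7). Appendix 1 has the start date agreed with the patient and sets no maximum wait. Against this, section 6.6.2, which section 6.7.2 carries into Phase 2, places the offer of a class place before consent.

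The SAP's primary model has baseline value, arm and hospital. Its repeated-measures model has arm, time point and their interaction. No visit window or elapsed-time term appears.

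**The concern.** The control visit is fixed by the calendar, while the intervention visit is fixed by the end of a programme whose length differs between sites. A hospital term absorbs differences between hospitals. It cannot absorb a difference between the two arms of the same hospital, and a categorical visit label treats week 8 and week 12 as the same time point.

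This matters because screening takes place about 6 weeks after surgery (section 6.6.2) and some patients are on chemotherapy, so activity, fatigue and quality of life are plausibly still changing. Section 6.2.3 intends the pilot to supply an estimate of intervention impact for sizing the definitive trial, and the SAP reports that estimate with confidence intervals and p-values. Cost differences are also to be tested between arms (section 6.9.2). If the rule passed into the definitive trial, a larger sample would not reduce the bias.

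The rule also gives no T1 date to randomised patients who never start classes or who stop early. Yet analysis is by intention to treat, and section 10.3 lets such patients keep providing data.

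**Working it through.** **Inputs.** Programme length L is 8 or 12 weeks (Protocol 6.4; SAP General Study Design and Plan). The control visit is at week 12. The wait w from baseline to first class is not given; 0 to 6 weeks is assumed. Expected recruits are 26 in Cardiff, 26 in Stirling and 14 in Inverness (section 6.2.3). There is no plan figure to reproduce.

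**Offset at a site.** Intervention minus control, in weeks since baseline, is L + w - 12. Both arms add three months to reach T2, so the T2 offset is the same.

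| | w = 0 | w = 2 | w = 4 | w = 6 |
|---|---|---|---|---|
| L = 8 | -4 | -2 | 0 | +2 |
| L = 12 | 0 | +2 | +4 | +6 |

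At an 8-week site with w = 0, T1 is week 8 against week 12. T2 is about week 21 against week 25 (taking three months as 13 weeks). If baseline is about 6 weeks after surgery, T1 is about 14 against 18 weeks after surgery.

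**Can it vanish everywhere?** With both lengths in use and a common wait, the two offsets are w - 4 and w. They differ by 4, so they cannot both be zero, and at least one is 2 weeks or more in size.

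**Average over the trial.** With f the share of patients at 8-week sites and w equal across sites, the mean offset is w - 4f. At w = 0:
- Inverness alone at 8 weeks: f = 14/66 = 0.212, mean -0.85 weeks.
- Cardiff and Stirling at 8 weeks: f = 52/66 = 0.788, mean -3.15 weeks.

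The average is zero at w = 0.85 and w = 3.15 weeks respectively, but individual sites then still differ from zero.

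**Effect size (assumed).** If outcomes recover by 0.01 to 0.05 SD per week, 4 weeks shifts the contrast by 4 x 0.01 = 0.04 to 4 x 0.05 = 0.20 SD. The standard error of a standardised difference with 33 per arm is about sqrt(2/33) = 0.25.

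**Consequence for planning.** Required n varies as 1/d². If the true effect were 0.3 SD (assumed), a shift of 0.1 SD against rehabilitation multiplies the planned n by (0.3/0.2)² = 2.25. The same shift in its favour multiplies it by (0.3/0.4)² = 0.56.

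**Service use.** Section 6.9.2 says "we will ask questions on frequency of use in the previous three months" at each assessment. At an 8-week site with w = 0, a 13-week recall at T1 reaches 13 - 8 = 5 weeks before baseline in the intervention arm and 13 - 12 = 1 week in controls. The windows are equal in length but cover different stages of recovery.

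**The case against.** The strongest reply is that this is an unpowered pilot. Eligibility, consent, recruitment, retention and completion rates do not depend on aligned timing, and estimates of variability should be little affected by a shift in the mean. That stands. What remains exposed is the effect estimate and the economic comparison, both of which the plan intends to use.

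A second reply is that short programmes and waiting time offset each other. That is true at an 8-week site, where a 4-week wait brings the gap to zero, and biases of opposite sign may partly cancel in the pooled estimate. Such cancellation would be accidental, and it would still distort the between-site comparisons planned in section 6.8.

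A third is that no systematic delay is documented. Section 6.6.2 has a place offered before consent. Recruitment to month 13 with classes to month 16 leaves about 13 weeks for the last recruit, hence about 1 week of slack at a 12-week site and 5 at an 8-week site. This limits the positive offsets, for late recruits at least. A short wait, however, is the case in which an 8-week site carries close to the full 4 weeks.

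A reader might also infer three stronger things that the documents do not support:
- That every between-arm difference is confounded. At a 12-week site with a prompt start the offset is zero.
- That a 10-week programme enters the contrast. It is stated only for Phase 1, which has no control arm.
- That controls gain QALYs from the calendar alone. With an assumed utility of 0.70 to 0.85, 4/52 of a year is 0.05 to 0.07 QALY. That arises only if QALYs are summed to each arm's own T2 with no wait, and neither document plans such a sum. Section 6.9.3 says only that the analysis is within-trial.

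**Conclusion.** The visit rule is wrong as written, with a limited reach. At any Phase 2 site where programme length plus wait differs from 12 weeks, the arms are measured at different times since baseline at T1 and T2, and the SAP neither reports nor adjusts for it. With both lengths in use and a common wait, this must happen at one site at least.

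The offset is -4 weeks at an 8-week site with a prompt start, and as large as the wait at a 12-week site. The resulting bias may go either way. Its size is not determinable from the documents: the 0.04 to 0.20 SD for 4 weeks rests on an assumed recovery rate, and the waits are unknown. If outcomes do not change over these weeks, there is no bias.

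**What to change.** **Design rule, for the protocol and any definitive trial.** Time T1 and T2 from randomisation, with the same target week and window for both arms within each centre, set from that centre's programme length plus its usual wait. Apply it to everyone randomised, whatever their attendance; this also gives non-starters and early stoppers a T1 date. Compute QALYs and costs over one common horizon. The cost is a wording change to the protocol, visit schedule and SAP, with no extra visits. The downside is that T1 may fall a week or two after an individual's last class.

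**Data already collected.** The SAP describes collection in the past tense, so only analysis changes remain for this trial:
- Report actual weeks from baseline and from randomisation to T1 and T2, by arm and centre.
- Add a sensitivity analysis that interpolates the outcomes of whichever arm was measured later back to the other arm's median assessment time at that centre. With three visits and about 33 patients per arm this will be rough, and it should be labelled so.
- State the caveat wherever the effect estimate is used to plan the definitive trial.

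**Passages to reconcile.** Sections 6.4 and 6.6 disagree on programme length (8 or 12 weeks against 10), and Stirling takes part in both phases. Sections 6.6.2 and 6.7.2 place the offer of a class before consent, while section 6.7 places referral after randomisation. The authors should settle both, because they determine L and w.
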